7.2 Serious Adverse Event (SAE)

Serious adverse events are any events that:

- Result in death

- Is life threatening, or places the participant at immediate risk of death from the event as it occurred
- Requires or prolongs hospitalization
- Causes persistent or significant disability or incapacity
- Results in congenital anomalies or birth defects
- Is another condition which investigators just to represent significant hazards

7.3 Unanticipated Problem (UP):

Defined by DHHS 45 CFR part 46 as any incident, experience, or outcome that meets the following criteria.

- unexpected, in terms of nature, severity, or frequency, given (a) the research procedures that are described in the protocol-related documents, such as the IRB-approved research protocol and informed consent document; and (b) the characteristics of the study population.
- related or possibly related to participation in the research (in this guidance document, possibly related means there is a reasonable possibility that the incident, experience, or outcome may have been caused by the procedures involved in the research);
- suggests that the research places participants or others at a greater risk of harm (including physical, psychological, economic, or social harm) than was previously known or recognized.

7.4 AE & SAE Collection and Reporting

Throughout the study the research team will monitor the occurrence of AE and SAE. Data will be collected if an instance occurs, and the PI will be notified. All AE data, such as onset date, resolution date, outcome and treatments given will be documented in the source documents and will be recorded in the EDC and analyzed for severity to follow reporting protocol if severity level.

Follow-up will occur using the provided safety monitoring form if AE occurs. The follow up will end either when the symptoms resolve or up to 30 days past the end of the study participation.

7.5 Risks and Discomforts:

Standard sterile precautions for surgical procedures will be utilized for the rotator cuff repair surgery, but with any surgery there is risk of infection, bleeding, and swelling. There will also be a small needle insertion hole into the humerus and the iliac crest for the bone marrow stem cell collection, which will be about the same size as an IV insertion. This may have some minor pain or swelling and there is a very minor risk of infection. Pain post procedure can occur but is usually self-limiting. Bruising may also

occur. As with any research involving patients there is the inherent risk of a breach in patient confidentiality though this will be minimized using participant code numbers and adherence to all HIPAA guidelines.

8 Data Management Procedures

All personal information is strictly confidential, and no names will be disclosed except as required by law. Data from cellular analysis and demographics will be compiled in Microsoft Excel. The spreadsheet will not contain protected health information as all compiled data will be de-identified. The spreadsheet will be stored in a secure password protected folder on a laptop that only the study Investigators will have access to and will be permanently deleted following publication of any and all manuscripts, if any, written as a result of this research. Records related to this study will be securely retained in a secure location for a period of 3 years after the completion of the study or longer as required by law. At that time, all records will be properly destroyed.

9 Data Analysis

A combination of Excel and SAS Studio (Version 3.8 on SAS 9.4, SAS Institute Inc., Cary, NC) will be used for data analysis. All compiled data will be de-identified.

10 Statistical Considerations

Descriptive statistics will be compiled for all numeral measures (Demographics, CBC, TNC, viability, CFU-F). Data will be analyzed for differences between experimental groups (PSIS v. deep humeral harvest, Prone vs. lateral decubitus positions) using 1-Way ANOVA and appropriate post-hoc analysis procedures (ex: Tukey's Honestly Significant Difference (HSD)). A significant p-value of < 0.05 for rejecting the null hypothesis will be used for all measures.

11 Quality Control and Assurance

All protocols will be monitored and analyzed data will be checked for accuracy by the principal investigator and /or a designated AREF research team member. All medical data will be kept in compliance with HIPAA guidelines.

12 References

1. Akpancar, S., et al., *The Current Perspectives of Stem Cell Therapy in Orthopedic Surgery*. Arch Trauma Res, 2016. **5**(4): p. e37976.
2. Marycz, K., et al., *Endurance Exercise Mobilizes Developmentally Early Stem Cells into Peripheral Blood and Increases Their Number in Bone Marrow: Implications for Tissue Regeneration*. Stem Cells Int, 2016. **2016**: p. 5756901.
3. Rochefort, G.Y., et al., *Multipotential mesenchymal stem cells are mobilized into peripheral blood by hypoxia*. Stem Cells, 2006. **24**(10): p. 2202-8.
4. Hauser, R.A. and A. Orloffsky, *Regenerative injection therapy with whole bone marrow aspirate for degenerative joint disease: a case series*. Clin Med Insights Arthritis Musculoskelet Disord, 2013. **6**: p. 65-72.
5. Hernigou, P., et al., *Biologic augmentation of rotator cuff repair with mesenchymal stem cells during arthroscopy improves healing and prevents further tears: a case-controlled study*. Int Orthop, 2014. **38**(9): p. 1811-8.
6. Hernigou, P., et al., *Cell therapy of hip osteonecrosis with autologous bone marrow grafting*. Indian Journal of Orthopaedics, 2008. **43**(1): p. 40-45.
7. Hernigou, P., et al., *Percutaneous autologous bone-marrow grafting for nonunions*. Journal of Bone and Joint Surgery, 2005. **87**(7): p. 1430-1437.
8. Saw, K.Y., et al., *Articular cartilage regeneration with autologous peripheral blood stem cells versus hyaluronic acid: a randomized controlled trial*. Arthroscopy, 2013. **29**(4): p. 684-94.
9. Vangsness, C.T., Jr., H. Sternberg, and L. Harris, *Umbilical Cord Tissue Offers the Greatest Number of Harvestable Mesenchymal Stem Cells for Research and Clinical Application: A Literature Review of Different Harvest Sites*. Arthroscopy, 2015. **31**(9): p. 1836-43.

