One cell therapy of interest currently involves bone marrow aspiration and concentration. Bone marrow aspiration and concentration is a method of progenitor cell harvest. Orthopedic surgeons have begun to augment surgical procedures and treat degenerative conditions such as osteoarthritis and cartilaginous injury with injections of concentrated bone marrow aspirate (cBMA) [4-8]. The use of cell therapies may contribute to decreased recovery time and morbidity rates [9-11]. Hernigou et al. showed significant improvement in patient outcomes could be achieved by the use of cBMA as an adjunct therapy in standard of care rotator cuff repair (RCR) [5]. In clinical application, studies have suggested that the success of these treatments is dependent on the total quantity and utility of harvested progenitor cells [5,7]. While bone marrow aspiration is frequently utilized for orthopedic point of care applications, the number of progenitor cells harvested is variable and dependent on body mass, aspiration technique, and location of harvest [5, 12]. Optimizing the harvest procedure is a key step in the development of bone marrow aspirate for orthopedic applications. Studies have attempted to find the most appropriate locations for harvesting bone marrow aspirate [13-17]. The preferred site for bone marrow extraction is the posterior iliac spine [13-17]. The posterior iliac spine yields the greatest concentration of viable nucleated cells when compared to the anterior iliac spine [13]. The posterior iliac spine also yields a greater concentration of nucleated cells when compared to other appendicular osseous sites, including the distal femur, proximal tibia, distal tibia, calcaneus, and proximal humerus [13-16]. In one study, the cBMA harvested from the posterior superior iliac spine (PSIS) resulted in a 3.0 times greater cellular yield and an 8.3 times greater proliferative cell product than cBMA from the proximal humerus [17]. Determining the quantity of progenitor cells in these samples can provide clinicians with a more cost-effective alternative for harvesting progenitor cells that can be used for surgical augmentation. However,

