the potential for progenitor cells to be harvested from the diaphysis of the humerus (deep humerus) has yet to be quantified. Thus, this the aim of this study is to analyze the cellular characteristics of cBMA from two extraction sites (PSIS and deep humerus) from patients undergoing standard-of-care arthroscopic rotator cuff repair surgery. Additionally, we aim to determine if patient positioning during PSIS harvest has any effect on the cellular content of collected cBMA.

2 Study Design

This is a single site, comparative quantitative analysis study of the cellular characteristics of bone marrow aspirate from two extraction sites (PSIS and deep humerus) from patients undergoing standard-of-care arthroscopic rotator cuff repair surgery. 30 total patients will be recruited through the Andrews Institute physician practices. Potential participants will be prescreened for inclusion and exclusion criteria through standard of care medical evaluations. Once a potential participant has agreed to be involved in the study, they will go through the described informed consent process. Patients meeting the inclusion criteria will have the study explained to them by one of the members of the research team, and they will be given an opportunity to participate if they are interested. No specific advertising or recruitment material will be utilized.

After the described screening and informed consent process have been completed, all participants will undergo standard-of-care arthroscopic rotator cuff repair surgery. During all surgeries, bone marrow will be aspirated from the PSIS and from the deep humerus. The first 15 participants will have bone marrow aspirated from the PSIS while in the prone position on the operating table. The final 15 participants will have bone marrow aspirated from the PSIS while in the lateral decubitus position on the operating table. Both cohorts will undergo deep humeral harvest intraoperatively in the lateral decubitus position. One mL of cBMA from each harvest site from each surgery will be removed and sent to the AREF Regenerative Medicine Center (RMC) for analysis. The remaining cBMA will be used to augment the rotator cuff repair surgery.

3 Objectives

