3.2 Secondary Objective

The secondary objective is to determine if prone verses lateral decubitus participant positioning influences the quantity of harvested cells from the PSIS.

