After the described screening and informed consent process have been completed, all participants will undergo standard-of-care arthroscopic rotator cuff repair surgery. During all surgeries, bone marrow will be aspirated from the PSIS and from the deep humerus. The first 15 participants will have bone marrow aspirated from the PSIS while in the prone position on the operating table and deep humerus during the surgery in the lateral decubitus position. The final 15 participants will have bone marrow aspirated from the PSIS while in the lateral decubitus position on the operating table and deep humerus during the surgery in the lateral decubitus position. Bone Marrow Aspirate will be concentrated at a 12% hematocrit setting independently from each site. One mL of cBMA from each harvest site from each surgery will be removed and sent to the AREF RMC for analysis. The remaining cBMA will be used to augment the rotator cuff repair surgery.

6.1 Surgical Procedure and cBMA Collection:

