viewing from the standard posterior portal in the subacromial space, a spinal needle will be used to localize the location and trajectory for placement of the first suture anchor for the rotator cuff repair. Once the placement of the proposed anterior suture anchor is confirmed, the 11-gauge bone marrow harvest needle will be placed into this location and the arm adducted. The needle will then be advanced into the humeral diaphysis as far as the needle length allows. Two 30 mL syringes will be pre-filled with 4 mL of ACD-A and used to harvest 60 mL of bone marrow aspirate. The bone marrow samples will then be processed independently using the Arthrex Angel blood processing system (Arthrex, Naples, FL) using the 12% hematocrit setting with two separate disposables. One mL of cBMA from each harvest site will be removed and sent to the AREF RMC for analysis. The remaining cBMA will be used to augment the rotator cuff repair surgery.

6.2 Cellular Analysis:

Cellular analysis of each cBMA sample from the two collection sites per participant will include a Complete Blood Cell (CBC) count, a Total Nucleated Cell (TNC), viability count, and cell culture analysis.

The CBC count will be performed using an automated hemocytometer (XN-350; Sysmex, Kungsbacka, Sweden) and will include red blood cell (RBC), white blood cell (WBC), monocyte, platelet, and hematopoietic progenitor cell (HPC) concentration.

The TNC and viability count will be performed using an automated cell counter.

Cell culture experiments will include Colony Forming Unit-fibroblast (CFU-F) counts and the potential for additional stem or progenitor cell analysis procedures. If stem or progenitor cells are observed during culturing, additional experiments will be conducted to analyze differentiation potential (differentiation assays) and cell-surface markers (flow cytometry).

7 Review of Safety

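### The primary site comparison is paired within patient, but section 10 of the protocol tests it with a 1-way ANOVA that has no patient term.

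*Protocol*

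**What the plan says.** The design is set out in sections 2, 6 and 6.2 of the protocol. Section 2 says "During all surgeries, bone marrow will be aspirated from the PSIS and from the deep humerus", and section 6 repeats it. On sampling, both sections say "One mL of cBMA from each harvest site from each surgery will be removed and sent to the AREF RMC for analysis". Section 6.2 describes the laboratory work as "Cellular analysis of each cBMA sample from the two collection sites per participant". Thirty patients therefore give 30 pairs, or 30 × 2 = 60 samples.

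The primary objective (section 3.1) is which site gives the greater cellular harvest. The secondary objective (section 3.2) is whether "prone verses lateral decubitus participant positioning influences the quantity of harvested cells from the PSIS". It compares the first 15 patients (prone) with the final 15 (lateral decubitus).

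Section 10 gives both questions the same test: "Data will be analyzed for differences between experimental groups (PSIS v. deep humeral harvest, Prone vs. lateral decubitus positions) using 1-Way ANOVA". It adds post-hoc procedures, with Tukey's HSD as the example, and a threshold of p < 0.05 for all measures. The protocol contains no paired test, repeated-measures term, patient effect or mixed model.

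**The concern.** Site is a within-patient factor and position is a between-patient factor, yet both are called experimental groups and sent to the same test. With two levels, a 1-way ANOVA is the independent-samples t-test. It leaves the variation between patients in the error term, although this design allows that variation to be removed.

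The direction of the error depends on the within-patient correlation.

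- **Positive correlation.** The test is conservative. A significant site difference remains valid, but a modest real difference may be missed. The null hypothesis in section 4.1 is that the sites have similar content, so a missed difference may be read as support for similarity.
- **Negative correlation.** The type I error exceeds 5%.

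The background section says that "the number of progenitor cells harvested is variable and dependent on body mass, aspiration technique, and location of harvest". Body mass is common to both samples of a patient, which makes a positive correlation plausible without establishing it.

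The missing pairing affects the site question only. Prone versus lateral on PSIS samples compares different patients, and a separate two-group ANOVA is valid there.

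**Working it through.** The protocol gives no effect size, SD or power calculation, so there is no stated figure to reproduce. The check is what the named test does with this design.

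**Inputs from the protocol:** 30 patients, one sample per site per patient, threshold 0.05 (taken as two-sided because the alternative in section 4.2 is non-directional).

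**Assumptions:** within-patient correlation ρ, shown over a range; equal SD at the two sites (SD = 1); normal data unless stated otherwise.

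**Step 1: standard error of the site difference.**

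- Used by the ANOVA: √(2/30) = 0.258 SD, whatever ρ is.
- True value: √(2(1 − ρ)/30), which is 0.216, 0.183 and 0.141 SD at ρ = 0.3, 0.5 and 0.7.
- Ratio: 1/√(1 − ρ) = 1.20, 1.41 and 1.83. The ANOVA standard error is too large by these factors.

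**Step 2: type I error and power.** Each ANOVA rate comes from 200,000 simulated trials of 30 pairs (58 df). Paired power and paired detectable differences come from the non-central distribution (29 df). The ANOVA detectable difference at ρ = 0 is exact; at other values it is found by simulation.

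| ρ (assumed) | ANOVA type I error | ANOVA power, 0.5 SD | Paired power, 0.5 SD | ANOVA: difference detectable at 80% | Paired: difference detectable at 80% |
|---|---|---|---|---|---|
| −0.2 | 7.3% | 48% | 40% | not computed | 0.82 SD |
| 0 | 5.0% | 48% | 47% | 0.74 SD | 0.75 SD |
| 0.2 | 2.9% | 47% | 55% | not computed | 0.67 SD |
| 0.3 | 2.1% | 47% | 61% | 0.70 SD | 0.63 SD |
| 0.5 | 0.7% | 47% | 75% | 0.67 SD | 0.53 SD |
| 0.7 | 0.1% | 46% | 93% | 0.64 SD | 0.41 SD |

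The paired test holds 5.0% type I error at every ρ. At ρ = −0.3 the ANOVA type I error is about 8.5%.

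**Step 3: larger differences.** At 0.8 SD and ρ = 0.3, 0.5 and 0.7, power is 90%, 93% and 97% with the ANOVA and 95%, 99% and 100% paired.

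**Step 4: skewed counts.** Lognormal data on the raw scale, with ρ on the log scale and an assumed CV:

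| CV, site ratio | ANOVA power at ρ = 0.3 / 0.5 / 0.7 | Paired power at ρ = 0.3 / 0.5 / 0.7 |
|---|---|---|
| 100%, 1.5 | 34 / 33 / 31% | 44 / 55 / 74% |
| 100%, 2 | 80 / 83 / 86% | 86 / 93 / 98% |
| 100%, 3.0 | about 99% | 99% or more |
| 150%, 3.0 | 85 / 87 / 89% | 88 / 93 / 97% |

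**Step 5: position.** A two-group ANOVA on PSIS samples, 15 against 15, has a simulated type I error of 5.0%. That test is sound.

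**The case against.** **A SAP could settle it.** Section 10 does not leave the test open. It names one, and a SAP would have to depart from the protocol to be right. If a repeated-measures ANOVA was meant, the text still needs correcting, because the same term covers the between-patient question.

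**Section 10 may intend one ANOVA over three groups** (PSIS prone, PSIS lateral, humerus). Tukey's HSD, which is needed only with three or more groups, points that way. This is a fair reading, and it changes the figures. At ρ = 0.5 the overall F-test has type I error of about 2% and about 34% power for a 0.5 SD site difference, and the Tukey contrast for position rejects about 1.9% of the time under its null. Patient is still ignored, so this reading does not rescue the plan. It does mean that the 5.0% for position holds only if position is tested separately.

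**The high correlations may be optimistic.** This stands in part. The same background sentence names aspiration technique and location, which differ between the sites and could weaken the correlation. At ρ = 0.2 the gain is only from 47% to 55%. Nothing in the protocol supports a negative correlation.

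**The consequence is limited.** This also stands in part. With positive correlation a significant result is safe, and at the 3.0-fold ratio cited for the proximal humerus the two tests differ little. But of the deep humerus the background says that "the potential for progenitor cells to be harvested from the diaphysis of the humerus (deep humerus) has yet to be quantified", so a modest difference cannot be excluded.

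**Conclusion.** The concern holds. The test that section 10 fixes for the primary objective does not match a design in which every patient provides both samples. This follows from the text and does not depend on any assumed number.

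The size does depend on the unknown within-patient correlation. Across 0.3 to 0.7 the ANOVA runs at roughly 2% down to 0.1% type I error, and it gives up about 14 to 46 percentage points of power for a 0.5 SD difference (61 − 47 and 93 − 47). At zero correlation the two tests are practically equal, so pairing costs almost nothing. The figures assume equal SDs and two separate two-level tests. The loss is mainly one of efficiency for modest site differences. It does not by itself invalidate a significant site result if the correlation is positive. It should be corrected before analysis, because it affects the site test of every primary-endpoint measure and a later change of test could look data-driven.

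**What to change.** Separate the two questions in section 10.

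- **Site (primary).** Suggested wording: *For each measure, PSIS and deep-humeral values will be compared within patient by a paired t-test on the 30 within-patient differences, or by a Wilcoxon signed-rank test where the distribution requires it, and the site difference will be reported with a 95% confidence interval.* A linear mixed model with a random patient effect and fixed site and position terms is an acceptable alternative. If site variances differ or the correlation may be negative, it should use an unstructured 2 × 2 within-patient covariance.
- **Position (secondary).** State that prone and lateral decubitus are compared on PSIS samples only, 15 against 15. The two-group 1-way ANOVA may stay for this question.
- **Post-hoc.** Remove the Tukey example. Each question then has two levels and needs no post-hoc test.

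A log scale for skewed counts is optional and is not part of the correction.

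The cost is a short rewording and a different procedure in the SAS software already named in section 9. The de-identified data set must keep the code that links a patient's two samples. No new patients, samples or measurements are needed.

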3.1 Primary Objective

The primary objective of this study is to determine whether the PSIS or deep humeral harvest produces a greater cellular harvest in patients undergoing rotator cuff repair.

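### Section 10 sends two planned two-level questions to a one-way ANOVA with Tukey-type post-hoc tests: the site test ignores patient pairing, and the post-hoc step is either empty or, in a layout the wording allows, costly.

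*Protocol*

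**What the plan says.** Section 3.1 sets the primary question: to "determine whether the PSIS or deep humeral harvest produces a greater cellular harvest in patients undergoing rotator cuff repair". Section 3.2 sets the secondary one: to "determine if prone verses lateral decubitus participant positioning influences the quantity of harvested cells from the PSIS". Under section 2, "30 total patients will be recruited", and every patient gives one sample from each site. The first 15 have the PSIS harvest prone and the last 15 in lateral decubitus. The humeral harvest is done in the same position in both cohorts.

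Section 10 carries the same two comparisons into the analysis: "Data will be analyzed for differences between experimental groups (PSIS v. deep humeral harvest, Prone vs. lateral decubitus positions"). The method is given as "using 1-Way ANOVA and appropriate post-hoc analysis procedures (ex: Tukey's Honestly Significant Difference (HSD"). The threshold is "A significant p-value of < 0.05 for rejecting the null hypothesis will be used for all measures".

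Section 10 does not say whether this means two separate two-group analyses or one ANOVA over several site-by-position cells. It does not mention that the two sites are sampled in the same patient.

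**The concern.** Each question has one contrast and one degree of freedom. A one-way ANOVA with post-hoc tests is built for a single factor with three or more independent groups, and neither question has that form.

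Two things are at stake. First, a one-way ANOVA treats the PSIS and humeral samples as coming from different people. Where cell yields in one patient are positively correlated, it uses too large a standard error for the primary comparison. Second, a post-hoc step has work to do only with three or more cells. If an analyst supplies those cells in order to use it, the primary question no longer has a single answer. PSIS prone and PSIS lateral are each tested against humerus, and one may be significant without the other. The position comparison, with only 15 patients a side, would also face a stricter threshold.

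**Working it through.** The protocol gives no effect size, SD, correlation or power figure, so there is nothing of its own to reproduce. Inputs from the protocol: 30 patients, two samples each, 15 prone and 15 lateral (section 2); threshold 0.05 (section 10), taken here as two-sided. Assumed: standardised differences d from 0.5 to 1.0, and within-patient correlation ρ from 0 to 0.7.

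**Reading A: two separate two-group analyses.** The two-group F equals t², and the Tukey critical value is q(0.95; k, df)/√2. With k = 2:
- Site, 58 df: Tukey 2.002, t 2.002.
- Position, 28 df: Tukey 2.048, t 2.048.

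The post-hoc step changes nothing. The remaining fault is the lack of pairing in the site test. The paired contrast has non-centrality d/√(2(1−ρ)/30). For d = 0.5 and ρ = 0.5 this is 0.5/√(1/30) = 2.74 on 29 df. The unpaired power and size below are simulated.

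| ρ | Unpaired power, d = 0.5 | Paired power, d = 0.5 | Unpaired true size (nominal 5%) |
|---|---|---|---|
| 0 | 48% | 46–47% | 5% |
| 0.3 | 47% | 61% | 2% |
| 0.5 | 47% | 75% | about 0.7% |
| 0.7 | 47% | 93% | about 0.1% |

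**Reading B: one ANOVA over three cells** (PSIS prone 15, PSIS lateral 15, humerus 30; 57 df). There are three pairs. The critical |t| is 3.403/√2 = 2.406, a per-pair level of 0.019. A planned contrast on the same error term needs 2.002.

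**Reading C: one ANOVA over four cells of 15** (site by cohort; 56 df). There are six pairs. The critical |t| is 3.745/√2 = 2.648, a per-pair level of 0.0105. Of the six pairs, two are same-cohort site comparisons and one is the position comparison. The other three (humerus against humerus, and two cross-cohort site pairs) answer no objective.

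Power by the non-central t, with non-centrality d/√(1/n₁ + 1/n₂):

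| Question | Single planned test | Tukey, 3 cells | Tukey, 4 cells |
|---|---|---|---|
| Position, 15 v 15, d = 1.0 (non-centrality 2.74) | 0.75 | 0.63 | 0.54 |
| Site, d = 0.8, pairing ignored | 0.86 (30 v 30) | 0.55 for each 15 v 30 pair | 0.33 for each 15 v 15 pair |

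The 0.75 is the two-sample t-test on 28 df; with the pooled error term it is 0.77.

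**How often the split site question gives a mixed answer.** In simulation at d = 0.74 and ρ = 0, at least one same-cohort site pair was significant in 67% of runs (3 cells) or 47% (4 cells). Both were significant in 29% or 8%. Exactly one was therefore significant in 67 − 29 = 38%, or 47 − 8 = 39%. The single 30 v 30 test has 80% power at the same d.

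**The case against.** The strongest objection is that the protocol never names a three- or four-cell model. Section 10 lists two comparisons, "PSIS v. deep humeral harvest, Prone vs. lateral decubitus positions", and these match the two objectives. The labels overlap, since every PSIS sample is also a prone or a lateral one, so they cannot be levels of one factor. That favours two separate analyses, in which Tukey costs nothing. The post-hoc phrase may be boilerplate, Tukey is only an example, and a statistical analysis plan not shown here could settle the layout. All of this stands. The losses under Readings B and C are therefore conditional.

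A reader might infer several stronger things that the document does not support:
- That the plan commits to all-pairs testing and will lose this power. It does not; the wording only permits it.
- That power is spent on comparisons nobody asked for. This is true only with four cells. With three, every pair bears on an objective, and the loss comes from splitting the site question and from the stricter threshold.
- That the Tukey loss would persist in any repeated-measures model. On a two-level site effect Tukey again equals t (2.045 at 29 df). A loss returns only if Tukey is applied to site-by-position cells.
- That Tukey is invalid for planned contrasts. It is conservative here, not wrong.
- That ignoring the pairing produces false positives. With positive correlation it does the opposite.

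The objection does not rescue the site test. On its own preferred reading, the named method still treats paired samples as independent. That is stated in the protocol, not left open.

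**Conclusion.** The point holds in a limited form. On the plainest reading the post-hoc step is redundant and harmless, and the material fault is the unpaired site test. Its size depends on a correlation that the protocol does not give. At ρ = 0 there is no loss; at ρ = 0.5 and d = 0.5, power is about 47% where a paired contrast has 75%. On the multi-cell reading, which is allowed but not stated, the primary question loses its single answer and the position comparison loses 0.12 to 0.21 of its power at an assumed 1 SD (0.75 to 0.63 or 0.54). On neither reading does the named method suit both objectives. The calculations assume normal data with equal variances. This is worth correcting before analysis, but it does not make the study's conclusions invalid.

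**What to change.** In section 10, replace the one-way ANOVA and post-hoc wording with two planned contrasts for each measure:

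1. Site: PSIS minus deep humerus within patient, by paired analysis or mixed model, as one overall contrast over all 30 patients.
2. Position: prone against lateral decubitus, PSIS samples only, as a two-sample comparison.

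Apply no all-pairs adjustment to these two contrasts, and show any other cell comparisons descriptively.

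The cost is a sentence or two in section 10 and slightly different SAS code, with no extra patients, samples or data. If the within-patient correlation turned out to be zero, pairing would cost about one percentage point of power (48% to 46–47% at d = 0.5).
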